2.2 Part B Objectives and Endpoints

Objectives	Endpoints	Justification for Endpoints
Primary		
To evaluate the safety and tolerability of the combination of fostamatinib and ruxolitinib in MF patients	Incidence, severity, frequency, and outcomes of AEs and SAEs as defined by CTCAE v5.0 criteria and AEs of interest (AEIs) as defined in section 5.5	The safety of this combination therapy in MF patients is not known.
Secondary		
To evaluate the spleen response in patients with MF receiving fostamatinib in combination with ruxolitinib	Spleen response as detailed in Section 11.4 after 12 weeks of combination therapy, mean reduction in spleen volume as determined by ultrasound after 12 weeks of combination therapy and at the end of treatment	The efficacy of fostamatinib in combination with a JAK inhibitor on reducing spleen size in patients with MF is unknown
To evaluate the impact of fostamatinib in combination with ruxolitinib on constitutional symptoms in patients with MF	Constitutional symptoms as detailed in Section 11.3 after 12 weeks of combination therapy and at the end of treatment	The efficacy of fostamatinib in combination with a JAK inhibitor on symptoms in MF is unknown
Evaluate the ability of fostamatinib to enable sustained treatment with ruxolitinib	Duration of uninterrupted JAK inhibitor (ruxolitinib) therapy	The ability of fostamatinib to maintain an adequate platelet count for patients

		to remain on JAK inhibitor therapy is unknown
To evaluate the impact of fostamatinib and ruxolitinib on marrow fibrosis	Change in marrow fibrosis per WHO grading on bone marrow biopsy performed at the end of fostamatinib and ruxolitinib therapy	The impact of fostamatinib and ruxolitinib combination therapy on marrow fibrosis is unknown

3.0 STUDY POPULATION

3.1 Inclusion Criteria

1. Confirmed diagnosis of primary myelofibrosis or post-polycythemia vera/essential thrombocythemia myelofibrosis classified as high risk, intermediate-2 risk, or intermediate 1 risk by IPSS.
2. Severe thrombocytopenia defined as platelet count $< 50,000/\text{microL}$ (confirmed on at least two measurements over an 8-week period prior to date of consent).
3. At least 18 years of age.
4. ECOG performance status ≤ 2 (see Appendix A)
5. Able to swallow pills
6. Adequate bone marrow and organ function as defined below:
 - a. ANC $\geq 1000/\text{microL}$
 - b. Peripheral blood blasts $\leq 10\%$
 - c. Albumin $> 2.7 \text{ g/dL}$
 - d. Total bilirubin $\leq 1.5 \times \text{IULN}$; patients with Gilbert's syndrome may enroll if direct bilirubin $\leq 1.5 \times \text{IULN}$
 - e. AST(SGOT)/ALT(SGPT) $\leq 1.5 \times \text{IULN}$
 - f. Creatinine clearance $> 30 \text{ mL/min}$ by Cockcroft-Gault
7. Female subjects must be either post-menopausal for at least 1 year or surgically sterile; or, if of childbearing potential, must not be pregnant or lactating and must agree to use a highly effective method of birth control throughout the duration of the trial and for 30 days following the last dose. Acceptable methods of birth control are defined as: hormonal contraception (pill, injection or implant) used consistently for at least 30 days prior to screening, an intrauterine device (IUD), or intrauterine hormone-releasing system (IUS), or true abstinence (i.e. abstinence is in line with the preferred and usual lifestyle of the subject.). Male subjects do not need to use contraception for fostamatinib because human studies showed minimal R406 in sperm.
8. Ability to understand and willingness to sign an IRB approved written informed

consent document (or that of legally authorized representative, if applicable).

3.2 Exclusion Criteria

1. History of allogeneic stem cell transplant.
2. Any solid tumor or hematologic malignancy (other than myelofibrosis) requiring active treatment at the time of study entry
3. Currently receiving any other investigational agents.
4. A history of allergic reactions attributed to compounds of similar chemical or biologic composition to fostamatinib, ruxolitinib, or other agents used in the study.
5. Uncontrolled intercurrent illness including, but not limited to, ongoing or active infection, symptomatic congestive heart failure, unstable angina pectoris, or cardiac arrhythmia.
6. Subject has uncontrolled or poorly controlled hypertension, defined as systolic blood pressure ≥ 130 mmHg or diastolic blood pressure ≥ 80 mmHg, whether or not the subject is receiving anti-hypertensive treatment.
7. Pregnant and/or breastfeeding. Women of childbearing potential must have a negative pregnancy test within 14 days of study entry and prior to the first dose of fostamatinib.
8. Known positive status for human immunodeficiency virus (HIV)
9. Chronic, active, or acute viral hepatitis A, B, or C infection, or hepatitis B or C carrier.
10. Treatment with strong CYP3A inhibitors or inducers within 14 days before the first dose of study drug. Strong CYP3A inhibitors and CYP3A inducers are not permitted during the study.
11. Ongoing gastrointestinal medical condition such as Crohn's disease, inflammatory bowel disease, or chronic diarrhea that is not well controlled and could interfere with absorption of oral medication or be exacerbated by study medication
12. Known hepatic cirrhosis or severe pre-existing hepatic impairment.
13. Uncontrolled coagulopathy or bleeding disorder.
14. Female patients who intend to donate eggs and male patients who intend to donate sperm during the course of this study or for 4 months after receiving the last dose of study treatment.

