1.3 Thrombocytopenia in MF and rationale for SYK inhibition

Thrombocytopenia is a hematologic complication of MF resulting from ineffective erythropoiesis as well as hypersplenism in the setting of splenomegaly. There are currently few effective therapies for the treatment of thrombocytopenia in MF. Treatment with ruxolitinib can further lower the platelet count, leading to dose attenuations that may limit the efficacy or prohibit continuation of the medication. Ruxolitinib (as well as Fedratinib) are also not recommended for patients with platelets < 50,000/microL, thereby limiting the treatment options for patients with MF with severe thrombocytopenia.

Fostamatinib is an oral spleen tyrosine kinase (SYK) inhibitor recently approved for the treatment of chronic idiopathic thrombocytopenic purpura (ITP), and may be a potential therapeutic option for patients with MF with severe thrombocytopenia. As hypersplenism from splenomegaly can be a contributing factor to thrombocytopenia in MF, an agent that blocks spleen tyrosine kinase signaling may improve the platelet count in these patients. Additionally, increasing the platelet count $\geq 50,000/\text{microL}$ would allow patients with severe thrombocytopenia to be treated with ruxolitinib. Another feature of fostamatinib is that there was no reported increased risk of thrombosis in the phase 3 studies [29], which makes it an attractive agent for patients with MF where thrombosis is a concern.

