5.7 Concomitant Therapy and Supportive Care Guidelines

General supportive care measures, including blood and platelet transfusions, antiemetics, administration of granulocyte colony-stimulating growth factors, corticosteroids, and use of antibiotics and antivirals are permitted at the discretion of the treating physician.

It is recommended that nausea, vomiting, diarrhea, or blood pressure elevation be medically managed according to the investigator's discretion.

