5.8 Prohibited Concurrent Therapy

Patients should not receive treatment with any potent CYP3A4 inhibitors for one week prior to the start of and for the duration of study treatment.

Other chemotherapeutic or investigational agents are not permitted while the patient is receiving active treatment on protocol.

The use of thrombopoietin (TPO) stimulating agents are not permitted while the patient is receiving active treatment on protocol.

Patients cannot receive radiotherapy within 14 days prior to study enrollment or while on study.

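### The Part A platelet response rate cannot separate a fostamatinib effect from recovery after stopping a platelet-lowering drug, because prior exposure is neither limited at entry nor accounted for in the analysis

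*Combined protocol and SAP*

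**What the plan says.** **Entry.** Inclusion criterion 2 (3.1) requires platelets below 50,000/microL, "confirmed on at least two measurements over an 8-week period prior to date of consent". It does not say what treatment the patient may be on when those counts are drawn.

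**Limits on drugs before entry.** Section 3.2 has two: exclusion 3, "Currently receiving any other investigational agents", and exclusion 10, "Treatment with strong CYP3A inhibitors or inducers within 14 days before the first dose of study drug". Section 5.8 adds intervals before entry for potent CYP3A4 inhibitors and for radiotherapy: "Patients cannot receive radiotherapy within 14 days prior to study enrollment or while on study". None of these names JAK inhibitors, cytoreductive drugs or TPO agents.

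**Limits during treatment.** Section 5.8 states "Other chemotherapeutic or investigational agents are not permitted while the patient is receiving active treatment on protocol" and "The use of thrombopoietin (TPO) stimulating agents are not permitted while the patient is receiving active treatment on protocol". Both begin with protocol treatment.

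**Endpoint.** Section 10.2.2 applies to patients whose baseline count has been under 50 × 10⁹/L for at least 8 weeks. It requires 50 × 10⁹/L or more on two measurements at least 2 weeks apart. The synopsis limits the primary endpoint to the first 12 weeks and names platelet transfusion as the only thing to be ruled out. The number of patients eligible to start ruxolitinib is also a Part A endpoint (synopsis, 2.1).

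**Mechanism.** Section 1.2 attributes myelosuppressive effects to JAK2 inhibitors, and section 1.3 says "Treatment with ruxolitinib can further lower the platelet count", to the point that the drug may have to be stopped.

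**The concern.** Part A has one arm and an absolute platelet threshold. Its response rate reads as a drug effect only if counts would otherwise have stayed below 50K. That is doubtful for a patient whose qualifying counts were depressed by a drug that is then withdrawn. Part A is single-agent fostamatinib, so a JAK inhibitor would be expected to stop at or before Cycle 1 Day 1. Any recovery could then fall within the 12 weeks in which the primary endpoint is read.

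Two results would be affected. The platelet response rate would include responses not due to fostamatinib. The count of patients made eligible for ruxolitinib would include some who had been taking a JAK inhibitor shortly before. In a hypothesis-generating pilot, the response estimate is the main thing carried forward to the next study.

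**Working it through.** **1. Does any rule close the gap?**

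| Rule | Would it catch a patient who qualified on a JAK inhibitor and stopped just before C1D1? |
|---|---|
| 3.1, criterion 2 | No. It asks for two low counts before consent, with no off-drug condition and no count required at C1D1. |
| 3.2, exclusion 3 | No. A commercially prescribed JAK inhibitor is not an investigational agent, and the rule covers current use only. |
| 3.2, exclusion 10, and the CYP3A4 rule in 5.8 | No. They concern CYP3A inhibitors and inducers. |
| 5.8, chemotherapeutic, investigational and TPO agents | No. These bans apply during protocol treatment only. |
| 5.8, radiotherapy | No. It is a different treatment. |
| 10.2.2, baseline under 50 for 8 weeks or more | In part. It screens out a brief dip, but 8 weeks of low counts on a drug still satisfy it. |

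Section 5.2 calls ruxolitinib investigational because it is combined with fostamatinib in this study. That does not bring earlier standard use under exclusion 3, which concerns *other* agents in current use.

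**2. The plan's own efficacy figures (12.4), n = 12, exact binomial.**

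- P(X ≤ 1 | p = 0.20) = 0.8¹² + 12 × 0.2 × 0.8¹¹ = 0.275. Stated: 27%.
- P(X ≥ 2 | p = 0.40) = 1 − 0.6¹² − 12 × 0.4 × 0.6¹¹ = 0.980. Stated: 98%.

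Both reproduce. The arithmetic in 12.4 is not in question.

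**3. Size of one misattributed response.** 1/12 = 8.3 percentage points. Exact (Clopper-Pearson) 95% intervals:

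| Responses of 12 | Rate | 95% CI |
|---|---|---|
| 0 | 0% | 0% to 26.5% |
| 1 | 8.3% | 0.2% to 38.5% |
| 2 | 16.7% | 2.1% to 48.4% |
| 3 | 25.0% | 5.5% to 57.2% |

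**4. Range for the expected bias (assumed inputs).** Let k of the 12 patients have recently stopped such a drug. Let each recover with probability r regardless of fostamatinib, and let p be the true fostamatinib response rate. Then the expected apparent rate = p + (k/12)(1 − p)r. Neither k nor r is in the documents. The value p = 20% is one of the scenarios in 12.4.

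| k | r | p = 0 | p = 20% |
|---|---|---|---|
| 0 | any | 0% | 20% |
| 2 | 0.10 | 1.7% | 21.3% |
| 3 | 0.10 | 2.5% | 22.0% |
| 3 | 0.25 | 6.3% | 25.0% |
| 6 | 0.50 | 25.0% | 40.0% |

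For example, with k = 3 and r = 0.25: 0.20 + 0.25 × 0.80 × 0.25 = 0.25. The bias runs from negligible to large, and the documents do not say where this trial would fall.

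**The case against.** **Exposure may be rare.** Section 1.2 says JAK inhibitors are generally not recommended in severe thrombocytopenia, 1.3 says the same of ruxolitinib below 50K, and the stated aim is to let patients *initiate* ruxolitinib. This stands and bears on the size of the problem. No criterion enforces it, however, and patients who had to stop ruxolitinib for low counts are natural candidates for this trial.

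**Recovery is not shown.** The documents give no rate or time course for platelet recovery after withdrawal. Section 1.3 also attributes the thrombocytopenia to the disease and to hypersplenism, which stopping a drug does not remove. This stands too: the plan permits the misattribution, but nothing shows that it would occur.

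**The 8-week condition in 10.2.2 and the confirmatory count help.** They protect against transient dips and isolated high values, but not against low counts sustained by a drug.

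Four stronger readings are tempting but not supported:

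- *The chance of a false positive trial rises sharply.* A reader might take two or more responses as success and compute, at a true rate of 5%, a rise from 11.8% to 1 − 0.95¹¹ = 43.1% once one recovery is taken as given. But 12.4 offers its figures as examples, 12.3 makes every analysis descriptive, and no success threshold is stated. The 5% rate and the certain recovery are both assumptions. The issue is bias in an estimate, not type I error.
- *Every platelet-active drug inflates the result.* A TPO agent stopped at entry would tend to lower counts on study and so bias against fostamatinib.
- *The protocol must impose a washout.* That would work as a treatment-stopping rule with a real cost to patients. The existing 14-day and 8-week intervals were not set for this purpose.
- *The response rate is already known to be biased.* The documents do not show that any exposed patient would be enrolled.

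**Conclusion.** The gap is real on the text: qualifying counts may be drawn on platelet-lowering drugs, no rule limits those drugs before entry, and the analysis plan does not identify the patients concerned. A recovery after withdrawal would be counted as a fostamatinib response and as ruxolitinib eligibility. Each such response is worth 8.3 percentage points in an estimate whose exact interval at 2/12 already runs from 2.1% to 48.4%.

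The total effect cannot be fixed from the documents. It depends on how many patients are recently exposed and how often they recover, and it may be small. The conclusion rests on the protocol's own account of JAK inhibitors as myelosuppressive and on the assumption that stopping one can let platelets rise. It does not call the design or the figures in 12.4 into question. It is a weakness of interpretation that is cheap to remedy and worth correcting.

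**What to change.** 1. At screening, record the last-dose date of any JAK inhibitor, cytoreductive or chemotherapeutic drug, or TPO agent. Concomitant medications are already collected at that visit, so this is one added field.
2. In 12.3, prespecify that the Part A platelet response rate and the number eligible to start ruxolitinib are each reported with exact 95% confidence intervals, first for all patients and again excluding those exposed to any of these agents during the 8-week qualifying window or between consent and C1D1. The second period is needed because screening evaluations may precede therapy by up to 3 weeks, and stopping a drug then would otherwise be missed.
3. State which agents were involved, since JAK inhibitors and TPO agents would bias in opposite directions.

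Whether to add an off-drug condition to eligibility, and of what length, is for the sponsor to decide.

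**Cost:** one data field, one extra table row and no effect on accrual. The restricted set has a wider interval. If two exposed non-responders were removed, 2/12 (2.1% to 48.4%) would become 2/10 (2.5% to 55.6%). If one exposed responder were removed instead, it would become 1/11 (0.2% to 41.3%).

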3.3 Inclusion of Women and Minorities

Both men and women and members of all races and ethnic groups are eligible for this trial.

4.0 REGISTRATION PROCEDURES

Patients must not start any protocol intervention prior to registration through the Siteman Cancer Center.

The following steps must be taken before registering patients to this study:

1. Confirmation of patient eligibility
2. Registration of patient in the Siteman Cancer Center database
3. Assignment of unique patient number (UPN)

4.1 Confirmation of Patient Eligibility

Confirm patient eligibility by collecting the information listed below:

1. Registering MD's name
2. Patient's race, sex, and DOB
3. Three letters (or two letters and a dash) for the patient's initials
4. Copy of signed consent form
5. Completed eligibility checklist, signed and dated by a member of the study team
6. Copy of appropriate source documentation confirming patient eligibility

4.2 Patient Registration in the Siteman Cancer Center OnCore Database

All patients must be registered through the Siteman Cancer Center OnCore database.

4.3 Assignment of UPN

Each patient will be identified with a unique patient number (UPN) for this study. All data will be recorded with this identification number on the appropriate CRFs.

4.4 Screen Failures

Screen failures are defined as participants who consent to participate in the clinical trial but are not subsequently entered in the study. A minimal set of screen failure information is required to ensure transparent reporting of screen failure participants, to meet the Consolidated Standards of Reporting Trials (CONSORT) publishing requirements and to respond to queries from regulatory authorities. Minimal information includes demography, screen failure details, eligibility criteria, and any serious adverse event (if applicable).

4.5 Strategies for Recruitment and Retention

The study will enroll 12 patients who are over 18 years of age of all genders, races, and ethnicities. The anticipated accrual rate will be approximately 1 patient per month. This pilot study will be a single center study and participants will be screened in the outpatient clinics of the PI and sub-investigators. Potential participants will be identified by the PI or sub-investigators and approached by the study coordinator(s) for the study. Financial compensation in the form of parking vouchers or reimbursement for travel expenses (ie gas, mileage, etc.) may be provided depending on the distance the participant may live from the study site.

5.0 TREATMENT PLAN

5.1 Premedication Administration

No pre-medications are required for either fostamatinib or ruxolitinib.

5.2 Study Intervention Description

Fostamatinib is a kinase inhibitor indicated for the treatment of thrombocytopenia in adult patients with chronic immune thrombocytopenia. It is considered investigational in this study.

Ruxolitinib is a kinase inhibitor indicated for the treatment of intermediate or high risk myelofibrosis, polycythemia vera, and steroid-refractory acute GVHD. Because it is being given in combination with fostamatinib, it is considered investigational in this study.

5.3 Study Intervention Administration

In Part A of the study, patients will initially receive fostamatinib single agent at a starting dose of 100 mg PO twice daily (BID) for three cycles (12 weeks). Each cycle is 28 days (4 weeks).

Patients who tolerate single agent fostamatinib and achieve a sustained platelet count of $\geq 50,000/\text{microL}$ on at least two separate measurements taken at least two weeks apart at any point before Cycle 10 Day 1 will be eligible to proceed to Part B of the study and initiate treatment with ruxolitinib (starting dose will be determined by platelet count as per package insert).

For patients who do not achieve a sustained platelet count of $\geq 50,000/\text{microL}$ following the first cycle (4 weeks) of fostamatinib 100 mg BID and no AEIs (see Section 5.5) are reported, then the dose of fostamatinib may be increased to 150 mg BID and continued for subsequent cycles. If a platelet count of $\geq 50,000/\text{microL}$ is not achieved after three cycles of fostamatinib, but the patient is achieving clinical benefit, then the patient may continue on fostamatinib monotherapy for up to a total of 12 cycles of treatment and may continue

on to Part B of the study if they achieve a sustained platelet count of $\geq 50,000/\text{microL}$ by Cycle 10 Day 1. If the patient is not achieving clinical benefit or has evidence of disease progression, then the patient will be taken off study.

For Part B of the study, patients will continue on treatment with fostamatinib for up to an additional nine cycles (36 weeks) to complete a total treatment duration of 48 weeks. Ruxolitinib will be initiated in combination with fostamatinib at the start of Part B unless the patient is experiencing progressive MF symptoms and is eligible to initiate ruxolitinib, in which case ruxolitinib may be initiated sooner at the discretion of the PI. If the platelet count decreases to $< 50,000/\text{microL}$ following initiation of ruxolitinib, then the dose of fostamatinib may be increased to 150 mg BID if the patient is on the 100 mg BID dose.

